4 STUDY DESIGN

Please refer to BMS' protocols MB130-068 and MB130-069 - IND 125297.

This study is a feasibility companion protocol that will rely on the data generated by BMS's studies of BMS-986036 (PEG-FGF21) under protocols MB130-068 and MB130-069 (IND 125297), which are defined in this companion protocol as two separate study cohorts (1 and 2, respectively) with the exception of the MBT, for which Exalenz may extract additional data based on the recorded MBT results. The MB130-068 and MB130-069 studies are Phase 2b, multicenter, double-blind, randomized, placebo-controlled, parallel-group studies to demonstrate the safety and efficacy of BMS-986036 in the treatment of subjects with NASH and stage 3 liver fibrosis or compensated cirrhosis with up to 48 weeks of treatment. The study is feasibility for drug response monitoring however the data may be used by Exalenz for future submissions.

As described in the BMS protocols, subjects will be enrolled and randomized via interactive response technology (IRT) to receive BMS-9860936 10mg QW, BMS-986036 20mg QW, BMS-9860936 40mg QW or matching placebo QW in a 1:1:1:1 ratio.

The BMS studies' treatment durations will each consist of two periods:

1. A 48-week, Double-Blind Treatment Period, during which the subjects will receive blinded study medication (BMS-986036 10mg, 20 mg, 40mg QW or matching placebo QW). During the Double-Blind Treatment Period, subjects will be evaluated for safety and efficacy every 4 weeks (± 5 days) through Week 24 and every 8 weeks (± 5 days) from Week 24 through Week 48.
2. A Follow up period, during which subjects will be evaluated for safety and efficacy for 4 weeks through Week 52.

Meridian Bioscience Israel Ltd.	Last update: May 05, 2021
SAP for Protocol BMS-EX-0118: Companion protocol for the ¹³C-Methacetin Breath Test (MBT) for use in Bristol-Myers Squibb phase 2b studies for BMS-986036 (PEG-FGF21), under Protocols MB130-068 and MB130-069	Document Version: 1.0
Document Nº: CSD00114	Page 12 of 21

3. A Follow up period of at least 6 months and up to 14 months after the Week 52/ PTFU Visit for the collection of additional DXA assessment (in all participants) and immunogenicity assessments (in participants for whom Long-Term Immunogenicity Follow-Up Visits are required.) Any liver related complication event will be recorded.

The last dose of study medication will be at the Week 48 visit. Subjects will have a safety and efficacy evaluation at week 48 and return for a post-treatment follow-up evaluation through Week 52.

As a sub-study of BMS protocols MB130-068 and MB130-069, MBT will be performed at the Day 1 visit and every 24 weeks during the Double-Blind Treatment Period in order to allow the assessment whether BMS-986036 compared to placebo improves liver metabolic function as determined by the MBT.

4.1 *Sample Size Considerations*

Subjects, that were enrolled into two separate BMS sponsored IND studies (MB130-068, MB130-069, respectively) at selected study sites, were offered the opportunity to perform the MBT, and are considered as two separate study cohorts (cohort 1 and 2, respectively) for this companion protocol. Each cohort consists of four treatment arms (BMS-986036 10mg, 20mg, 40mg QW or matching placebo QW) as defined in the respective BMS sponsored protocols.

Cohort 1 consists of subjects with NASH and stage 3 fibrosis, as assessed by a central laboratory reader of the liver biopsies, and who meet all the MB130-068 study criteria. The sample size for this MB130-068 study is n=160.

Cohort 2 consists of subjects with NASH and compensated liver cirrhosis (stage 4 fibrosis) as assessed by a central laboratory reader of the liver biopsies, and who meet all the MB130-069 study criteria. The sample size for this MB130-069 study is n=100.

This feasibility companion protocol includes those two cohorts of subjects, which were planned for up to 260 subjects) from approximately 75 sites worldwide (USA and Japan) for the two BMS IND studies, while the MBT was only conducted in the USA.

It was expected that not all participating sites would elect to perform the MBT. The total number of subjects expected to perform the MBT was initially planned for up to 250 subjects (also accounting for drop outs). Each subject would perform up to 3 MBTs over 1 year.

Meridian Bioscience Israel Ltd.	Last update: May 05, 2021
SAP for Protocol BMS-EX-0118: Companion protocol for the ¹³C-Methacetin Breath Test (MBT) for use in Bristol-Myers Squibb phase 2b studies for BMS-986036 (PEG-FGF21), under Protocols MB130-068 and MB130-069	Document Version: 1.0
Document Nº: CSD00114	Page 13 of 21

However, as aforementioned in the Introduction (section 2), the enrollment phase and all MBT testing (incl. Day1, Week 24 and Week 48 visits) for the aforementioned BMS sponsored studies has been completed. The data is still being assessed by BMS and the respective databases are planned to be made available to Exalenz between July and November 2021, after their respective data lock and release from BMS.

The initially planned sample size of 250 subjects, per statistical section in the companion protocol, was not reached for multiple reasons:

- The MBT testing as part of the BMS studies, was an opt in substudy, requiring an additional consent process. Subjects enrolled to the BMS studies were reluctant to add an additional investigational test to their study schedule.
- The COVID-19 outbreak further complicated the enrollment and especially the follow up testing of already enrolled subjects, as visits were more and more conducted remotely and any breath testing was avoided during in person visits.

Since the actual final sample size of subjects with valid MBT results at baseline and post-treatment phase, across both BMS studies, is expected to be lower than 80, the statistical analyses for the study will be descriptive by nature. No formal statistical testing will be performed. Nominal p-values from statistical tests will be reported for supplementary information.

5 GENERAL CONSIDERATIONS FOR HANDLING OF MISSING DATA

5.1 *Premature Withdrawal and Missing Data*

For patients who are withdrawn from the study prior to study completion, all data compiled up to the point of discontinuation will be used for analysis. All withdrawals will be included in all analyses up to the time of withdrawal.

There will be no imputation for missing data.

The study variables cannot be evaluated for subjects for whom BreathID® MCS device MBT results are not available and therefore these subjects will be left out of the efficacy analysis. Subjects missing clinical outcome or biopsy results or other endpoints will be excluded from the respective analyses.

Meridian Bioscience Israel Ltd.	Last update: May 05, 2021
SAP for Protocol BMS-EX-0118: Companion protocol for the ¹³C-Methacetin Breath Test (MBT) for use in Bristol-Myers Squibb phase 2b studies for BMS-986036 (PEG-FGF21), under Protocols MB130-068 and MB130-069	Document Version: 1.0
Document Nº: CSD00114	Page 14 of 21

6 SIGNIFICANCE LEVELS AND HANDLING OF TYPE I ERROR

6.1 *Type I Error*

All analyses in this study will be considered descriptive by nature. No formal statistical testing will be performed. Nominal p-values from statistical tests will be reported for supplementary information.

7 ANALYSIS SETS

7.1 *Safety Analysis Set (SA)*

The Safety Analysis set will include all subjects enrolled under BMS' MB130-068 and MB130-069 studies that initiated at least one MBT (had taken the ¹³C-Methacetin solution), even if the MBT was not completed or the result was not valid.

7.2 *Efficacy Analysis Set (EA)*

The Efficacy Analysis set will include all subjects enrolled under BMS' MB130-068 and MB130-069 studies who have successfully performed the MBT test and did not have any major protocol deviations for the current study.

7.3 *Modified Efficacy Analysis Set (mEA)*

The modified Efficacy Analysis set will include all subjects enrolled under BMS' MB130-068 and MB130-069 studies who have successfully performed the MBT test. Visit specific major protocol deviation will be excluded, while keeping subjects in this analysis set for other valid visits.

Safety analyses will be performed on the SA set and efficacy analyses on the mEA set. Sensitivity analysis will be performed on the SA (corresponding to ITT) and EA set.

Meridian Bioscience Israel Ltd.	Last update: May 05, 2021
SAP for Protocol BMS-EX-0118: Companion protocol for the ¹³C-Methacetin Breath Test (MBT) for use in Bristol-Myers Squibb phase 2b studies for BMS-986036 (PEG-FGF21), under Protocols MB130-068 and MB130-069	Document Version: 1.0
Document Nº: CSD00114	Page 15 of 21

8 STATISTICAL ANALYSES

8.1 *General Considerations for Data Analyses*

All analyses will be performed using either SAS® v9.4 or higher (SAS Institute, Cary NC, US) or the R software version 4.0.3 or higher (R Development Core Team. Vienna, Austria).

The standard summary statistics for continuous variables are: N, mean, standard deviation, median, minimum and maximum. The standard summary statistics for categorical variables are: count and proportion.

The analyses will be descriptive by nature, nominal p-values will be reported for supplementary information. Any statistical tests performed, will be two-sided. The significance level of findings will be equal to or lower than 5%. Where confidence limits are appropriate, the confidence level will be 95%. Nominal p-values and unadjusted confidence intervals will be presented.

8.2 *Baseline Definitions*

The study baseline will be defined as the Day 1 visit value, unless specifically mentioned otherwise. In case of repeat measurements, the latest value associated with the Day 1 visit will be considered the baseline value.

For survival models: The baseline MBT test will be defined as the baseline and day 0 of follow up.

8.3 *Disposition of Patients*

Subject dispositions will be summarized based on all subjects screened into the study separated by study cohort (and combined), and for each treatment group.

The following subject disposition information will be presented:

- The number and percentage of subjects who had valid MBT for each visit.
- The number and percentage of reasons for not having a valid MBT for each visit.
- The number and percentages of subjects that were excluded from the EA and mEA analysis sets, by reason for exclusion.

Meridian Bioscience Israel Ltd.	Last update: May 05, 2021
SAP for Protocol BMS-EX-0118: Companion protocol for the ¹³C-Methacetin Breath Test (MBT) for use in Bristol-Myers Squibb phase 2b studies for BMS-986036 (PEG-FGF21), under Protocols MB130-068 and MB130-069	Document Version: 1.0
Document Nº: CSD00114	Page 16 of 21

8.4 *Efficacy Analyses*

8.4.1 *Primary Endpoint*

In order to show the ability of the MBT to measure the effect of BMS-986036 treatment on the metabolic capacity of the liver after Week 24 and Week 48 visits, as compared to changes in placebo treated subjects, the primary endpoint will be analyzed using a responder analysis, where any increase of MBT value will be considered as a response while a same value or a decrease of the MBT value will be considered as non-response.

The primary analysis will be conducted on the mEA set, with the PDR_{peak} and cPDR₃₀ responder rate of Week 24 and Week 48 of data from both BMS' studies.

Individual analyses for each cohort separately will also be reported.

8.4.2 *Secondary Endpoints*

8.4.2.1 *Prognostic Value of MBT in Overall Event-Free Survival*

In order to assess the prognostic value of MBT in prediction of liver disease deterioration (reported as liver-related clinical outcome events), the endpoint measures will be point estimates of Cox Regression's Hazard Ratio for classifying Subjects into risk groups for clinical deterioration with respective exact two-sided 95% confidence intervals in the placebo and treatment arms as determined by MBT. The MBT parameter to be used to predict liver-related clinical outcome events is PDR_{peak}. Any PDR_{peak} value of less or equal to 20 %/h (see **Appendix A** for detailed description of parameter calculation) will be considered as 'high risk' and any value above that threshold will be considered as 'lesser risk' (additional cut-off values may be explored). The dichotomic MBT result will be tested for significance using the Cox proportional hazards regression model with site and randomized arm as covariates. If the randomized arm factor is found non-significant (i.e. p-value > 0.05), then this factor will not be a covariate for the main analysis to be performed. If the randomized arm factor is found statistically significant (i.e. p-value ≤ 0.05), then the main analysis will be performed keeping this factor as a covariate (to 'adjust' the analysis for treatment).

The time-to-first event will be derived as the number of days between the Day 1 MBT test and the date when the first event occurs or when a subject is censored (i.e., event/censored date minus

Meridian Bioscience Israel Ltd.	Last update: May 05, 2021
SAP for Protocol BMS-EX-0118: Companion protocol for the ¹³C-Methacetin Breath Test (MBT) for use in Bristol-Myers Squibb phase 2b studies for BMS-986036 (PEG-FGF21), under Protocols MB130-068 and MB130-069	Document Version: 1.0
Document Nº: CSD00114	Page 17 of 21

Day 1 MBT date plus 1). Subjects will be censored at their last study visit for the following reasons:

- If a subject discontinues the study prior to the end of the study without experiencing an event
- If a subject reaches the Final Treatment visit without experiencing an event

Survival analysis will be conducted using the Cox proportional hazard model. The model summary will include the number of subjects in the model, and a table with each covariate in a separate line specifying the coefficient's value, Hazard Ratio, Hazard Ratio 95% Confidence Interval and p-value. In addition, a Kaplan-Meier plot for event-free survival will be presented, stratified by MBT parameter along with the MBT parameter log-rank p-value. Additionally, a crosstab table of MBT parameter and events will be presented.

8.4.2.2 Correlations between changes in MBT parameters and changes in other liver related parameters

Repeat MBT results (cPDR₃₀, PDR_{peak} or other breath test parameters) and their changes in subjects with and without treatment (BMS-986036) for nonalcoholic steatohepatitis (NASH) at Day 1, Week 24 and Week 48 (or Early Termination visits) will be compared and tested for correlation to baseline, as well as repeat results (change from baseline), for the following measurements:

- a. Biopsy based Fibrosis and/or NAS score
- b. Liver stiffness as measured by MRE
- c. PDFF as measured by MRI
- d. Serum Pro-C3 results
- e. Liver elastography by Fibroscan (in cohort 2 only)
- f. MELD scores (in cohort 2 only)
- g. CTP scores (in cohort 2 only)

Linear Regression will be applied in order to test for significance of the correlations between MBT and the liver measurements listed above.

Changes in MBT are measured as the difference between baseline and each of the MBT visits as well as the change in measurements between two subsequent visits in each of the two treatment groups.

Meridian Bioscience Israel Ltd.	Last update: May 05, 2021
SAP for Protocol BMS-EX-0118: Companion protocol for the ¹³C-Methacetin Breath Test (MBT) for use in Bristol-Myers Squibb phase 2b studies for BMS-986036 (PEG-FGF21), under Protocols MB130-068 and MB130-069	Document Version: 1.0
Document Nº: CSD00114	Page 18 of 21

The metabolic capacity of the liver as determined by the MBT PDR_{peak} and cPDR₃₀ will be the main MBT parameters of interest.

Nevertheless, available breath test parameters (Delta Over Baseline - DOB at the respective times) will be collected from the completed eCRFs. The DOBs will be transformed to percentage dose recovery – PDR, by normalizing the DOB using patient weight and height. The Area under the DOB and under the PDR curve will be calculated at 5-minute time intervals resulting in cDOB and cPDR at 5, 10, 15, 20, 25, 30, 35, 40, 45, 50, 55 and 60 minutes respectively. Analyses may be done using any of the MBT derived parameters.

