7.7.8 Child-Turcotte-Pugh (CTP) Scoring

The Child-Turcotte-Pugh (CTP) score assesses the severity of cirrhosis and will be done for cohort 2 Subjects. It has been shown to be an accurate measure across a broad spectrum of liver disease. It employs numerical scores of 5 measures of liver disease: total bilirubin, serum albumin, international normalized ratio for INR, ascites, and encephalopathy and is scored according to the scheme in Appendix 8 of study protocols MB130-068 and MB130-069. The sum of scores from each component is the final score.

Blood samples will be collected for the total bilirubin, serum albumin, and prothrombin time assessments used to calculate the CTP score as part of the hematology and serum chemistry assessments conducted at each visit. The same central laboratory will be used for each evaluation. Evaluations of ascites and encephalopathy are to be conducted by the same site personnel at each visit wherever possible.

CTP scores will be determined at each study visit.

7.7.9 ¹³C-Methacetin Breath Test (MBT)

The ¹³C-Methacetin Breath Test (MBT) is a non-invasive tool that provides an estimate of liver function by assessing microsomal capacity to metabolize the non-radioactive ¹³C-labeled Methacetin. MBT measures carbon dioxide exhaled into a nasal cannula before and after drinking a non-radioactive solution (called ¹³C-methacetin), using a device called the BreathID® MCS device. The amount of ¹³carbon dioxide (¹³CO₂) exhaled over 60-85 minutes will then be measured. The MBT, which consists of both a device and an unapproved drug component, is considered an investigational device that has not been reviewed, approved or cleared by the FDA for marketing purposes.

In Subjects evaluated/listed for liver transplantation, a reduction in exhaled ¹³CO₂ has been associated with an increased risk of cirrhotic complications ⁽³⁾. MBT will be conducted at selected sites in subjects who provide consent. The test will be performed after an 8-hour fast according to study guidelines and as per the manufacturer's instructions.

MBT will be conducted at Day 1 visit prior to first dose of treatment, week 24 and week 48. For participants discontinuing study treatment at sites selected for the MBT sub-study, MBT should be conducted only if the date of discontinuation is more than 12 weeks from the date of the previous MBT.

| | |
|---|---|
| Exalenz Bioscience Ltd. | Last update: February 20, 2018 |

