9.6 Statistical Analysis

9.6.1 General Considerations

Statistical analyses will be performed using R software version 3.4.3 or higher (R Development Core Team. Vienna, Austria).

If any statistical tests are performed, they will be two-sided. The required significance level of findings will be equal to or lower than 5%. Where confidence limits (CL) are appropriate, the confidence level will be 95%.

| | |
|---|---|
| Exalenz Bioscience Ltd. | Last update: February 20, 2018 |
| Study Title: Companion protocol for the ¹³C-Methacetin Breath Test (MBT) for use in Bristol-Myers Squibb phase 2b studies for BMS-986036 (PEG-FGF21), under Protocols MB130-068 and MB130-069 | Protocol: BMS-EX-0118 Version: 1.0 |
| Document No: CSP000002 | Page 32 of 38 |

Baseline values are defined as the last valid value prior to investigational treatment start. Study data will be summarized by descriptive statistics. Continuous variables will be summarized by a mean, standard deviation, minimum, median and maximum, and categorical variables by a count frequency and percentage. Confidence intervals will be provided where relevant.

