10.2 Breath Test Procedure

Preparation of the study subject

Once consented, the Subjects will perform the breath test on day 1 prior to first dose treatment, at 24 and 48 weeks of treatment prior to dose uptake and biopsy procedure if relevant. In preparation for each breath test the patient will be asked to comply with the following precautions:

1. Subject should be fasting, including all oral morning medications (except for beta-blockers and study drug [BMS-986036 or placebo]), for at least 8 hours prior to the test
2. Subject should not smoke on the day of the breath test prior to the breath test
3. Subject should not take any of the following drugs within 48 hours prior to the test: acyclovir, allopurinol, carbamazepine, cimetidine, ciprofloxacin, daidzein (herbal), disulfiram, echinacea, enoxacin, famotidine, fluvoxamine, methoxsalen, mexiletine, montelukast, norfloxacin, phenylpropanolamine, phenytoin, propafenone, rifampin, terbinafine, ticlopidine, thiabendazole, verapamil, zileuton or any medication that might interfere with methacetin metabolism or might affect CYP1A2 (cytochrome P450 1A2)
4. Subject should not take amiodarone within 30 days prior to the test

| | |
|---|---|
| Exalenz Bioscience Ltd. | Last update: February 20, 2018 |
| Study Title: Companion protocol for the ¹³C-Methacetin Breath Test (MBT) for use in Bristol-Myers Squibb phase 2b studies for BMS-986036 (PEG-FGF21), under Protocols MB130-068 and MB130-069 | Protocol: BMS-EX-0118 Version: 1.0 |
| Document No: CSP000002 | Page 34 of 38 |

5. Subject should not take paracetamol (acetaminophen) related medications within the 24 hours prior to the test
6. Subject should not perform the test if allergic or hypersensitive to Methacetin or its metabolites (paracetamol, acetaminophen)
7. Subject should not consume any alcohol or caffeine within 24 hours prior to the test
8. Subject should not have general anesthesia or sedation within 24 hours prior to the test
9. Subjects on beta-blockers or statins should be on a stable dose at least 30 days prior to the test

Preparation of ¹³C-Methacetin

Exalenz Bioscience Ltd. will provide 75 mg ¹³C-Methacetin doses in a 0.05% solution of ¹³C-Methacetin in purified water, supplied, in amber thermoplastic polyester (PET) bottles with a child resistant plastic cap. No preparation is needed other than pouring the contents of the solution into a cup for ingestion.

Performance of the breath test

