6. If at any time the device does not detect patient's breath, or if there is any other deviation from the desired test requirements, the device will produce an appropriate warning message on the screen.
7. At the completion of the MBT, the device screen will indicate that the test is completed and a printout will be generated. The IDcircuit is then removed and the patient is disconnected from the BreathID® MCS device.

The patient will be under the supervision of the physician or any other qualified medical staff during the entire test.

The operators will be trained how to terminate the breath test early. In the following situations, the MBT will be terminated and a termination form will be completed:

1. The patient vomits after ingestion of the substrate.
2. The BreathID® MCS device malfunctions (in this case, the operator will complete a technical complaint form in addition to the termination form and contact Exalenz immediately for further instructions) after ingestion of the substrate.

In all these cases, MBT cannot be repeated the same day for that specific subject that has already ingested ¹³C-Methacetin. Efforts should be made to repeat the MBT on one of the subsequent days. An entry will be made in the drug/kit accountability log and the ¹³C-Methacetin bottles will be kept for inspection by the study monitor.

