SAP for Protocol BMS-EX-0118: Companion protocol for the ¹³C-Methacetin Breath Test (MBT) for use in Bristol-Myers Squibb phase 2b studies for BMS-986036 (PEG-FGF21), under Protocols MB130-068 and MB130-069	Document Version: 1.0
Document Nº: CSD00114	Page 8 of 21

for the study will be descriptive by nature. No formal statistical testing will be performed. Nominal p-values from statistical tests will be reported for supplementary information.

When differences exist in methods, descriptions or explanations provided in the protocol and this SAP, the SAP prevails.

Since this study is a companion to a pharmaceutical company's study, the data management for the main study can independently determine as to when a data freeze or a data lock shall be performed. Therefore, for the Exalenz companion protocol purposes, any amendments to the SAP will be made prior to Exalenz independently accessing the data from the database freeze or lock, if available. In case additional analyses not described in the final SAP or deviations from the final SAP are required, they will be documented in the Clinical Study Report (CSR).

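### SAP 8.2 drops the protocol's pre-treatment condition on baseline, so a repeated Day 1 breath test taken after the first dose could serve as baseline

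*SAP*

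**What the plan says.** Protocol 9.6.1 sets two conditions, validity and timing: "Baseline values are defined as the last valid value prior to investigational treatment start".

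SAP 8.2 replaces this with a visit label: "The study baseline will be defined as the Day 1 visit value, unless specifically mentioned otherwise". For repeats it adds: "In case of repeat measurements, the latest value associated with the Day 1 visit will be considered the baseline value". Neither sentence mentions validity or the first dose. SAP section 2 settles which text governs: "When differences exist in methods, descriptions or explanations provided in the protocol and this SAP, the SAP prevails".

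The scheduled Day 1 test is meant to be pre-dose. Protocol 7.7.9 says "MBT will be conducted at Day 1 visit prior to first dose of treatment, week 24 and week 48", and Protocol 10.2 says "the Subjects will perform the breath test on day 1 prior to first dose treatment".

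Protocol 10.2 also covers tests terminated because of vomiting or device malfunction after ingestion: "In all these cases, MBT cannot be repeated the same day for that specific subject". It continues: "Efforts should be made to repeat the MBT on one of the subsequent days".

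**The concern.** The repeat rule in SAP 8.2 comes into play only when a Day 1 test has been repeated. For a test terminated after ingestion, the repeat is never on the scheduled day. If the first dose has been given in the meantime and the repeat is still filed under the Day 1 visit, the governing rule takes the post-dose value as baseline.

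That baseline feeds the primary analysis. SAP 8.4.1 counts any rise over baseline in PDRpeak or cPDR30 at Week 24 or Week 48 as a response, with no minimum change, so a modest baseline shift can change a subject's classification. If the drug moves MBT within days, part of its effect would sit in the baseline of affected active-arm subjects. Placebo subjects have no drug effect to absorb.

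**Working it through.** **Comparing the texts**

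| Question | Protocol | SAP |
|---|---|---|
| Must the baseline precede treatment? | Yes (9.6.1) | Not stated (8.2) |
| Must the baseline value be valid? | Yes (9.6.1) | Not stated in 8.2; largely kept elsewhere (5.1, 7.3, 8.5) |
| Which value if repeated? | The last that meets both conditions | The latest filed under Day 1 |
| Must a repeat precede the first dose? | Not stated (10.2) | Not stated |
| Is a post-dose Day 1 test named a major deviation? | No | No (7.2, 7.3) |

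The two definitions agree when the scheduled Day 1 test succeeds. They can part when the test is terminated after ingestion, repeated after the first dose, and the repeat is labelled Day 1. In that case the protocol leaves the subject without a valid pre-dose MBT, while the SAP supplies a post-dose one.

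**Weight of one subject**

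Neither document gives a figure to reproduce here. SAP 4.1 expects fewer than 80 subjects with valid baseline and post-treatment MBT, and SAP section 4 gives 1:1:1:1 allocation in the parent studies. Equal arms in the sub-study are an assumption. One reclassified subject moves an arm's responder rate by 100 / (N/4) points:

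- N = 79: 100 / 19.75 = 5.1 points
- N = 60: 100 / 15 = 6.7 points
- N = 40: 100 / 10 = 10 points

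**Expected shift, illustration only**

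Assume that the true change in an active arm is normal with mean μ and SD 1, that a post-dose baseline is raised by d, and that a share f of the arm is affected. The shift in expected responder rate is f × [Φ(μ − d) − Φ(μ)]. None of μ, d or f is in the documents.

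- Smallest case: μ = 0.5, d = 0.1, f = 5%. 0.05 × (0.655 − 0.691) = −0.0018, a fall of about 0.2 points.
- Middle case: μ = 0.25, d = 0.25, f = 10%. 0.10 × (0.500 − 0.599) = −0.0099, a fall of about 1.0 point.
- Largest case: μ = 0.25, d = 0.5, f = 20%. 0.20 × (0.401 − 0.599), a fall of about 4.0 points.

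Over μ of 0.25 to 0.5, d of 0.1 to 0.5 and f of 5% to 20%, the fall is about 0.2 to 4.0 points in an affected active arm.

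**The case against.** The strongest reply is that the protocol twice places the Day 1 MBT before dosing and the SAP does not change that schedule. On this view, SAP silence about timing is not a difference that lets the SAP override the protocol. This holds for the scheduled test. It does not cover the repeat, for which 10.2 sets no such limit, and the two baseline definitions do differ on their face.

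A second reply is that the SAP has a safeguard: the modified efficacy set drops visits with a major deviation, and a post-dose Day 1 test is a natural candidate. This is partial protection, because neither document classes such a test that way.

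Third, first-dose and visit-window rules sit in the parent protocols MB130-068 and MB130-069, which are not part of this review and might close the gap. This stands. The point is that the companion documents leave the matter open, not that post-dose baselines occurred.

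Several stronger readings are tempting but unsupported:

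- **The SAP abandons validity.** It mostly does not. The primary set requires a successful test, SAP 5.1 leaves out subjects without MBT results, and SAP 8.5 refers to valid baseline results. Validity is loose mainly in the sensitivity analysis on the safety set (7.1, 7.3).
- **Every change score is affected.** Week 24 to Week 48 MBT change uses no baseline. Changes in biopsy, MRE, PDFF, Pro-C3 and Fibroscan are taken from screening.
- **The bias runs against the drug.** That needs an early rise in MBT after the first dose, and the documents give no onset data.
- **Every arm shifts by about 5 points.** The mechanism cannot act through placebo, an equal shift in all arms would leave the contrast with placebo unchanged, and an affected subject does not necessarily flip.
- **The survival origin is also biased.** SAP 8.2 and 8.4.2.1 start the clock at the MBT itself, which is coherent for a prognostic marker. A repeat moves the origin by days.

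**Conclusion.** The point holds as a defect in the governing baseline rule. SAP 8.2 omits the protocol's explicit pre-treatment condition, and the later-day repeat procedure gives a route by which a post-dose MBT could become baseline for the change-from-baseline and responder analyses.

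Distortion of response in the active arms depends on three things the documents do not establish: that a repeat fell after the first dose, that it was labelled Day 1, and that the drug changes MBT that early. The number of affected subjects is not given and is probably small, since the protocol calls vomiting rare. The figure of about 5 points is the effect of one flipped subject in an arm of 19 to 20, not an expected bias.

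All analyses are descriptive (SAP 6.1), which limits the stakes. Descriptive estimates still need a defined baseline, and fixing it now avoids a choice made after the data are seen.

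**What to change.** In SAP 8.2, define the MBT baseline for change-from-baseline and responder analyses as the last valid MBT obtained before the first dose of study drug. State that a Day 1 repeat obtained after the first dose is not a baseline. For a subject with no valid pre-dose MBT, set baseline to missing in those analyses, and add a flagged sensitivity analysis that uses the post-dose repeat. Report how many subjects are concerned. Reconcile the wording with the repeat-test text in Protocol 10.2. Leave the survival time origin unchanged.

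The change is to the analysis rule only. SAP section 2 allows amendments until the sponsor accesses the data, and the SAP of May 2021 expects the databases between July and November 2021. The cost is a few sentences and the possible loss of baseline for a few subjects in a sample already expected to be below 80. The sensitivity analysis shows whether that loss matters.
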